Figure 2:	Study Design Schematic (IgAN Cohort)	18

VERSION HISTORY

This statistical analysis plan (SAP) for Study ALXN2050-NEPH-201 is based on Protocol Amendment 3.0, dated 21 Feb 2024.

SAP Version	Version Date	Change	Rationale
1.0	23 Nov 2022	Not applicable	Original version.
2.0	10 May 2023	Included the option to perform an early interim analysis	For Phase 3 planning purposes.
		Other minor edits	For clarity.
3.0	12 Nov 2024	Deleted data presentation for Safety Follow-up Period	Safety Follow-up Period is not a treatment period.
		Revised the derivation of the primary endpoint	Visit window is changed.
		Added ALXN2050 Total group into data presentation	To evaluate the overall ALXN2050 treatment effect.
		Changed terminologies: "background therapy" to "allowed concomitant therapy" and "rescue therapy" to "additional standard-of-care therapy"	To align with EU CTR requirements.
		Added an analysis of abnormal liver enzyme elevations	To evaluate drug-induced liver injury.
		Added a sensitivity analysis due to dosing pause	Screening, enrollment, and study intervention administration have been temporarily paused as of 06 September 2024.
		Other minor edits	For minor corrections.

APPROVAL SIGNATURES

Biostatistics	Date dd Mmm yyyy
Biostatistics	Date dd Mmm yyyy
	Date dd Mmm yyyy

LIST OF ABBREVIATIONS

Abbreviation	Definition
AE	adverse event
ALP	alkaline phosphatase
ALT	alanine aminotransferase
AP	alternative pathway
AST	aspartate aminotransferase
ATC	anatomical therapeutic chemical
Bb	Bb fragment of complement factor B
bid	twice daily
BLQ	below the limit of quantification
Clq	complement component C1q
C3	complement component 3
C4	complement component 4
CDF	cumulative distribution function
CI	confidence interval
CNI	calcineurin inhibitor
COVID-19	coronavirus disease 2019
CRR	complete renal response
cTTO	composite time trade-off
CV	coefficient of variation
CV%	coefficient of variation percentage
dsDNA	double-stranded DNA
EC	exclusion criteria
ECG	electrocardiogram
eCRF	electronic case report form
eGFR	estimated glomerular filtration rate
EQ-5D-5L	5-level EuroQol-5 Dimensions
FACIT-Fatigue	Functional Assessment of Chronic Illness Therapy – Fatigue Scale
FAS	Full Analysis Set
FD	factor D
GM	geometric mean
GMR	geometric mean ratio
hpf	high power field
IC	inclusion criteria
IE	intercurrent event

Abbreviation	Definition	
IgAN	immunoglobulin A nephropathy	
LLN	lower limit of normal	
LN	lupus nephritis	
MAR	missing-at-random	
MCS	Mental Component Summary	
MedDRA	Medical Dictionary for Regulatory Activities	
mFAS	Modified Full Analysis Set	
MEST-C	mesangial, endocapillary hypercellularity, segmental sclerosis, interstitial fibrosis/tubular atrophy-presence of crescents	
MI	multiple imputation	
MMF	mycophenolate mofetil	
MNAR	missing not at random	
OLE	open-label extension	
ORR	overall renal response	
PCS	Physical Component Summary	
PD	pharmacodynamic(s)	
PK	pharmacokinetic(s)	
PPS	Per-Protocol Set	
PRR	partial renal response	
PT	Preferred Term	
QoL	quality of life	
RAS	renin-angiotensin system	
RBC	red blood cell	
SAE	serious adverse event	
SAP	statistical analysis plan	
SAS®	Statistical Analysis Software®	
SF-36	36-item Short Form Health Survey	
SLE	systemic lupus erythematosus	
SLEDAI-2K SELENA Modification	Systemic Lupus Erythematosus Disease Activity Index Safety of Estrogen in Lupus Erythematosus National Assessment Modification	
SOC	System Organ Class	
SOP	Standard Operating Procedure	
TEAE	treatment-emergent adverse event	
TESAE	treatment-emergent serious adverse event	
TTO	time trade-off	

Abbreviation	Definition
ULN	upper limit of normal
UP	urine protein
UPCR urine protein-to-creatinine ratio	
VAS	visual analog scale
WHO-DRUG	World Health Organization Drug Dictionary

1. INTRODUCTION

This statistical analysis plan (SAP) describes the statistical methods for analyzing data for Protocol ALXN2050-NEPH-201, "A Phase 2, Randomized, Double-blind, Placebo-controlled, Dose-finding Study to Evaluate the Efficacy and Safety of ALXN2050 in Adult Participants with Proliferative Lupus Nephritis (LN) or Immunoglobulin A Nephropathy (IgAN)." Standard data presentation instructions and table, figure, and listing specifications are contained in the Data Presentation Plan (DPP) in a separate document.

The objectives of this study are to evaluate the efficacy and safety of oral ALXN2050 compared to placebo, demonstrate proof of concept for efficacy of FD inhibition, and establish a dose in participants with LN or IgAN.

The primary efficacy analysis will be performed for each disease-specific cohort at the end of the 26-week Blinded Initial Evaluation Period after all participants in the disease-specific cohort have completed or withdrawn from the 26-week Blinded Initial Evaluation Period. This analysis will allow for evaluation of the primary endpoint and Phase 3 planning and will have no impact on the progression of this study. The sponsor will be unblinded at this time to conduct the primary analysis. After completion of the 26-week Blinded Initial Evaluation Period, participants in the LN cohort will continue receiving their randomized allocation of study intervention, and both the participants and the investigative site personnel will remain blinded for the remaining 24-week Blinded Extended Treatment Period.

An additional analysis will be performed for each disease-specific cohort at the end of the 24-week Blinded Extended Treatment Period after all participants in the disease-specific cohorts have completed Week 50 or withdrawn from the study.

The final analysis will occur at the end of the 2-year Open-label Extension (OLE) Period after all participants have completed the Safety Follow-up Visit and will include all planned analyses that will be presented in the final clinical study report.

Screening, enrollment, and study intervention have been paused as of 06 Sep 2024. Sensitivity analyses due to dosing pause are added into the relevant sections.

1.1. Objectives, Endpoints, and Estimands

Table 1: Objectives and Endpoints

Objectives	Endpoints	
Primary (Both Cohorts)		
To evaluate the efficacy of ALXN2050 to reduce proteinuria in participants with LN or IgAN	Percentage change in proteinuria from baseline to Week 26 (based on 24-hour urine collection[s])	

Table 1: Objectives and Endpoints

Objectives	Endpoints
Secondary (Both Cohorts)	
To evaluate the efficacy of ALXN2050 to improve measures of kidney function in	Percentage change in proteinuria from baseline to Week 50 (based on 24-hour urine collection[s])
participants with LN or IgAN	Achieving > 30% and > 50% reduction in proteinuria at Weeks 26 and 50 compared to baseline (based on 24-hour urine collection[s] at each time point)
	Change from baseline in eGFR at Weeks 26 and 50
Secondary (LN Cohort Only)	
To evaluate the efficacy of ALXN2050 on measures of kidney function in participants with	Meeting the criteria for complete renal response (CRR) at Weeks 26 and 50
LN	Meeting the criteria for partial renal response (PRR) at Weeks 26 and 50
	Time to the first occurrence of UPCR \leq 0.5 g/g as measured by spot urine sample
	Achieving corticosteroid taper to 7.5 mg/day at Weeks 12, 26, and 50
	Experience of a renal flare through Week 50
	Experience of an extrarenal systemic lupus erythematosus (SLE) flare through Week 50
	Meeting the criteria for treatment failure through Week 50
	Meeting the criteria for suboptimal response through Week 50
	Absolute values and change from baseline in serum albumin at Weeks 26 and 50
Secondary (IgAN Cohort Only)	
To evaluate the efficacy of ALXN2050 on measures of kidney function in participants with IgAN	Meeting the criteria for partial remission at Weeks 26 and 50
PK/PD (Both Cohorts)	
To characterize the pharmacokinetics (PK) and pharmacodynamics (PD) of ALXN2050 in	Observed plasma concentrations of ALXN2050 over time
participants with LN or IgAN	Absolute values and change from baseline in plasma Bb concentration and serum AP activity over time

Table 1: Objectives and Endpoints

Objectives	Endpoints		
Safety			
To characterize the safety and tolerability of	Incidence of TEAEs and TESAEs over time		
ALXN2050 in participants with LN or IgAN	Changes from baseline in laboratory assessments		
Exploratory (Both Cohorts)			
To assess the efficacy of ALXN2050 in exploratory efficacy endpoints	Percentage change in proteinuria from baseline to Weeks 102 and 154 (based on 24-hour urine collection[s])		
	Change from baseline in eGFR at Weeks 102 and 154		
To evaluate the efficacy of ALXN2050 on hematuria in participants with LN or IgAN	Absolute value and change from baseline in RBC in urine from baseline to Weeks 26 and 50		
	Achieving < 10 RBC/hpf		
To assess quality of life based on participant- reported outcomes in participants with LN or	Change from baseline in SF-36v2 at Weeks 26 and 50		
IgAN based on treatment with ALXN2050	Change from baseline in EQ-5D-5L at Weeks 26 and 50		
To evaluate biomarkers such as complement, autoimmune, and renal in participants with LN or IgAN	Absolute values and change from baseline in levels of biomarkers in blood and urine over time		
Exploratory (LN Cohort Only)			
To assess the efficacy of ALXN2050 in	Time to the first CRR or PRR (using spot UPCR)		
exploratory efficacy endpoints	Meeting the criteria for overall renal response (CRR or PRR) at Weeks 26 and 50		
	Time to the first occurrence of UPCR > 50% decrease from baseline (using spot UPCR)		
To assess quality of life based on participant- reported outcomes	Change from baseline in FACIT-Fatigue total score at Weeks 26 and 50		
To assess the efficacy of ALXN2050 in other exploratory endpoints	Histology changes from baseline to Week 50, if tissue is available		
	Absolute values and change from baseline in anti-dsDNA and anti-C1q antibodies at Weeks 26 and 50		
Exploratory (IgAN Cohort Only)			
To assess the efficacy of ALXN2050 in exploratory efficacy endpoints	Slope of eGFR computed from baseline to Weeks 26 and 50		
	•		

Abbreviations: anti-C1q = anti-C1q complement component; anti-dsDNA = anti double-stranded DNA; AP = alternative pathway; Bb = Bb fragment of complement factor B; CRR = complete renal response; eGFR = estimated glomerular filtration rate; EQ-5D-5L = 5-level EuroQol-5 Dimensions; FACIT-Fatigue = Functional Assessment of Chronic Illness Therapy – Fatigue Scale; IgAN = immunoglobulin A nephropathy; LN = lupus nephritis; PD = pharmacodynamic; PK = pharmacokinetic(s); PRR = partial renal

Table 1: Objectives and Endpoints

Objectives	Endpoints

response; RBC = red blood cells; SF-36v2 = 36-item Short Form Health Survey version 2; SLE = systemic lupus erythematosus; TEAE = treatment-emergent adverse event; TESAE = treatment-emergent serious adverse event; UPCR = urine protein-to-creatinine ratio

Primary Estimand

The estimand is described by the following attributes:

- Population: Full Analysis Set (FAS)
- Endpoint: Percentage change from baseline to Week 26 in proteinuria
- Treatment: ALXN2050 180 mg bid versus placebo
- Intercurrent events: Receipt of additional standard of care therapy (LN cohort only) or treatment discontinuation
- Population-level summary: Difference in mean percentage change in proteinuria between ALXN2050 180 mg bid and placebo groups

1.2. Study Design

Study ALXN2050-NEPH-201 is a Phase 2, randomized, double-blind, placebo-controlled, multicenter study of ALXN2050 in addition to allowed concomitant therapy consistent with the standard of care in adult participants (≥ 18 to ≤ 75 years of age) with either LN or IgAN.

All participants must have a diagnosis of LN with an active flare based on kidney biopsy or IgAN based on kidney biopsy, estimated glomerular filtration rate (eGFR) > 30 mL/min/1.73 m², and proteinuria defined as urine protein-to-creatinine ratio (UPCR) \geq 1 g/g from one 24-hour urine collection for LN and defined as mean protein \geq 1 g/24 hours from 2 valid 24-hour urine collections for IgAN. Participants with IgAN must have been treated with stable doses of the maximum tolerated renin-angiotensin system (RAS)-inhibiting medications and have controlled, stable blood pressure (< 140/90 mmHg) for \geq 3 months prior to Screening.

The study consists of an up to 6-week Screening Period, a 26-week Blinded Initial Evaluation Period, a 24-week Blinded Extended Treatment Period, and an OLE Period of up to 2 years. In addition, all participants will be followed for safety for 30 days after the last dose of study intervention. Thus, the total treatment duration is 154 weeks, and the total study duration is up to 164 weeks (Figure 1 and Figure 2).

All participants, Investigators, and site personnel will remain blinded to treatment assignment from Day 1 through the end of the 24-week Blinded Extended Treatment Period (ie, Week 50). During the OLE Period, participants, Investigators, and site personnel will no longer be blinded to treatment assignment. In this study, the independent Data Monitoring Committee will be responsible for review of efficacy and safety data.

Eligible participants will be assigned to a treatment arm by stratified randomization (approximately 70 participants in the LN cohort and approximately 56 participants in the IgAN cohort). For each disease cohort, participants will be randomly assigned in a 3:1:3 ratio to receive ALXN2050 180 mg bid, ALXN2050 120 mg bid, or placebo bid, respectively, during the

26-week Blinded Initial Evaluation Period. The LN cohort will continue with the same treatment allocation during the 24-week Blinded Extended Treatment Period (ALXN2050 180 mg bid, ALXN2050 120 mg bid, or placebo bid). For the IgAN cohort, participants assigned to the placebo group will also be assigned to their active study treatment for the 24-week Blinded Extended Treatment Period (ALXN2050 120 mg bid or ALXN2050 180 mg bid) in a 1:1 allocation ratio at the time of initial randomization.

The randomization stratum is defined as follows:

[figure not shown]
- LN cohort: corticosteroid induction treatment initiation (prior to Screening, during Screening Period)
- IgAN cohort: mean proteinuria from 2 valid 24-hour urine collections (1 to 2 g/day, > 2 g/day)

During the OLE Period, participants in both cohorts receiving ALXN2050 during the 24-week Blinded Extended Treatment Period will continue their active treatment at the same dose level. Once an optimal dose is identified based on results of the primary analysis at Week 26 for each cohort and/or Data Monitoring Committee review of the safety and efficacy data, all participants in that cohort with at least 50 weeks of study treatment will receive the optimal dose of ALXN2050. Participants in the LN cohort randomized to the placebo group will no longer receive placebo and will continue to receive allowed concomitant therapy alone. These participants will have the option to receive ALXN2050 180 mg bid or the optimal dose (if already identified) if the participant has a renal flare or suboptimal response.

In the LN cohort, participants who meet the criteria for protocol-defined renal flare or for extrarenal systemic lupus erythematosus (SLE) flare will receive additional standard of care therapy. After Week 26, participants may also receive additional standard of care therapy for protocol-defined suboptimal response. The specific choice of additional standard of care therapy(ies) is generally at the discretion of the Investigator.

Participants who discontinue study intervention and remain on study may receive treatment consistent with local standard practice for their disease per Investigator judgment.

[figure not shown]
Figure 1: Study Design Schematic (LN Cohort)

- ^a The optimal dose level will be identified based on the results of the Week 26 primary analysis. Once identified, all participants on active treatment who have at least 50 weeks of treatment will receive the selected optimal dose for the remainder of the study.
- b Participants will receive additional standard of care therapy in the event of a protocol-defined renal flare, or severe extrarenal SLE flare. Approved novel treatments for LN can be used per the Investigator's discretion. After Week 26, additional standard of care therapy for participants with suboptimal response is allowed at the clinical discretion of the Investigator in conversation with the Medical Monitor. However, if a CNI is used, ALXN2050 will need to be discontinued 3 days prior to CNI administration.
- ^c After completion of the 24-week Blinded Extended Treatment Period, participants in the placebo group will only receive allowed concomitant therapy during the Open-label Extension Period and will have the option to receive ALXN2050 180 mg bid or the optimal dose (if already identified) if the participant has a renal flare or suboptimal response.

Abbreviations: bid = twice daily; CNI = calcineurin inhibitor; LN = lupus nephritis; SLE = systemic lupus erythematosus

Figure 2: Study Design Schematic (IgAN Cohort)

- ^a The optimal dose level will be identified based on the results of the Week 26 primary analysis. Once identified, all participants who have at least 50 weeks of treatment will receive the selected optimal dose for the remainder of the study.
- At randomization, participants assigned to the placebo group will also be assigned to their study treatment for the 24-week Blinded Extended Treatment Period (ALXN2050 180 mg bid or ALXN2050 120 mg bid) in a 1:1 allocation ratio. After completion of the 26-week Blinded Initial Evaluation Period (Week 26), these participants will continue on ALXN2050 treatment during the 24-week Blinded Extended Treatment Period.

Abbreviations: bid = twice daily; IgAN = immunoglobulin A nephropathy

2. STATISTICAL HYPOTHESES

The primary hypothesis for this study is that ALXN2050 180 mg bid is superior to placebo in decreasing proteinuria. Hypothesis testing will be 1-sided and performed at the 0.05 level of significance for each disease cohort without adjusting for multiplicity.

2.1. Multiplicity Adjustment

There will be no adjustment for multiplicity.

3. ANALYSIS SETS

The participant analysis sets are defined as follows in Table 2:

 Table 2:
 Participant Analysis Sets

Participant Analysis Set	Description			
Randomized Set	The Randomized Set includes all randomized participants. Participants will be analyzed as randomized for reporting disposition, demographics, and baseline characteristics.			
Full Analysis Set (FAS)	Participants who have been randomized and received at least 1 dose of study intervention will be included in the FAS. Participants in FAS will be analyzed as randomized for reporting efficacy data.			
Modified Full Analysis Set (mFAS)	All FAS participants excluding participants who were impacted by coronavirus disease 2019 (COVID-19) as follows: 1. Participants who missed > 20% of total ALXN2050 dose amount assigned per protocol after the scheduled dosing time point during the 26-week Blinded Initial Evaluation Period due to COVID-19 2. Participants who withdrew early from the study during the 26-week Blinded Initial Evaluation Period due to COVID-19. 3. Participants who received concomitant treatments for COVID-19 during the 26-week Blinded Initial Evaluation Period that could potentially affect efficacy 4. Participants who were hospitalized due to a COVID-19 related adverse event during the 26-week Blinded Initial Evaluation Period Inclusion in the mFAS will be determined for each participant prior to			
Per-Protocol Set (PPS)	database lock. Participants to be included in the PPS need to meet all the following criteria: • For the LN cohort, satisfy the following specific inclusion criteria (IC)/exclusion criteria (EC): ○ IC No. 9: Active focal or diffuse proliferative LN Class or IV confirmed by biopsy obtained ≤ 6 months prior to Screening or during Screening Period ○ IC No. 10: Clinically active LN at Screening requiring/receiving immunosuppression induction treatment ○ IC No. 11: Proteinuria with UPCR ≥ 1 g/g based on one 24-hour urine collection ○ EC No. 28: Received any of the specified treatments defined in Protocol Section 5.2.2 ○ EC No. 29: Uncontrolled hypertension (systolic blood pressure > 160 mmHg or diastolic blood pressure > 110 mmHg) on 2 or more measurements			

 Table 2:
 Participant Analysis Sets

Participant Analysis Set	Description			
	 EC No. 30: Prior history or clinically active SLE-related cerebritis, seizures, pericarditis, stroke, or stroke syndrome requiring treatment For the IgAN cohort, satisfy the following specific inclusion criteria (IC) or exclusion criteria (EC): IC No. 12: Established diagnosis of primary IgAN based on kidney biopsy 			
	 IC No. 13: Mean proteinuria ≥ 1 g/day on 2 complete and valid 24-hour urine collections 			
	 IC No. 15: Compliance with stable and optimal dose of RAS inhibitor treatment 			
	 IC No. 16: Controlled and stable blood pressure (defined as < 140/90 mmHg) 			
	 EC No. 35: Prednisone or prednisone equivalent > 20 mg/day for > 14 consecutive days or any other systemic immunosuppression within 6 months prior to Screening 			
	o EC No. 37: Body mass index ≥ 38 kg/m² during Screening			
	 For both cohorts, satisfy the following criteria: 			
	 Participants who have an eGFR > 30 mL/min/1.73 m² during Screening 			
	 Participant informed consent/assent was provided prior to study procedures being carried out 			
	 Received correct treatment per randomization schedule Remained blinded to treatment allocation during the 26-week Blinded Initial Evaluation Period 			
	 Received > 80% of planned dose of study intervention during the 26-week Blinded Initial Evaluation Period 			
	 Received appropriate allowed concomitant therapy during the 26-week Blinded Initial Evaluation Period 			
	 Received appropriate additional standard of care therapy, if required by protocol, during the 26-week Blinded Initial Evaluation Period (LN cohort only) 			
	 Did not receive any disallowed medications or therapies considered having significant impact on the primary efficacy measure during the 26-week Blinded Initial Evaluation Period (defined in Protocol Section 6.5.2) 			
	The PPS will be determined prior to database lock.			
Safety Set (SS)	All participants who received at least 1 dose of study intervention will be included in the SS. Participants will be analyzed according to the study intervention they actually received for reporting exposure and safety data.			
	The SS is the primary analysis for all safety and exposure analyses.			

 Table 2:
 Participant Analysis Sets

Participant Analysis Set	Description
Pharmacokinetic (PK) Analysis Set	All randomized participants who received at least 1 dose of study intervention and who have a baseline PK value and at least 1 evaluable postdose PK assessment will be included in PK Analysis Set.
Pharmacodynamic (PD) Analysis Set	All randomized participants who received at least 1 dose of study intervention and who have a baseline PD value and at least 1 evaluable postdose PD assessment will be included in PD Analysis Set.

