4.2.4. Supplementary Analyses

Table 5 summarizes the supplementary analyses that will be produced for the primary endpoint.

The purpose of these supplementary analyses is to provide additional insights for the primary efficacy results in selected groups of the study population.

Table 5: Supplementary Analyses

Supplemental Analysis	Applied Cohorts	Population	Handling of IEs	
Randomized Set analysis	LN and IgAN cohorts	Randomized Set	 Analysis and handling of IEs will be the same as in the primary analysis Only performed if the FAS excludes more than 10% of the Randomized Set 	
mFAS analysis	LN and IgAN cohorts	mFAS	 Analysis and handling of IEs will be the same as in the primary analysis Only performed if the mFAS excludes more than 10% of the FAS 	
PPS analysis	LN and IgAN cohorts	PPS	Analysis and handling of IEs will be the same as in the primary analysis	
Treatment policy analysis	LN and IgAN cohorts	FAS	The primary endpoint will be analyzed in the same manner as in the primary analysis except that all observed data will be used, regardless of receipt of additional standard of care therapy (LN cohort only) or treatment discontinuation	

Abbreviations: FAS = Full Analysis Set; IE = intercurrent event(s); IgAN = Immunoglobulin A Neuropathy; mFAS = Modified Full Analysis Set; PPS = Per-Protocol Set

In addition, the same ANCOVA model as described in Section 4.2.2 will be used for the primary efficacy analysis to compare reductions in proteinuria between the ALXN2050 Total and placebo groups.

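### The COVID-19 missed-dose rule for the modified Full Analysis Set is written on ALXN2050 dose, so read literally it cannot exclude a placebo participant or be applied blind

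*SAP*

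**What the plan says.** SAP Section 3, Table 2, introduces the mFAS as "All FAS participants excluding participants who were impacted by coronavirus disease 2019 (COVID-19) as follows". Four criteria follow.

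- **Criterion 1** removes "Participants who missed > 20% of total ALXN2050 dose amount assigned per protocol", counted after the scheduled dosing time, with the limit "during the 26-week Blinded Initial Evaluation Period due to COVID-19".
- **Criterion 2** removes "Participants who withdrew early from the study during the 26-week Blinded Initial Evaluation Period due to COVID-19".
- **Criterion 3** removes "Participants who received concomitant treatments for COVID-19 during the 26-week Blinded Initial Evaluation Period that could potentially affect efficacy".
- **Criterion 4** removes those hospitalised for a COVID-19 adverse event in the same period.

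Membership is to be settled for each participant before database lock.

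In the same table, the Per-Protocol Set has a compliance condition for both cohorts that begins "Received > 80% of planned dose of study intervention", also over the first 26 weeks.

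The mFAS has one planned use for the primary endpoint. SAP Section 4.2.4, Table 5, repeats the primary analysis on it, under the condition "Only performed if the mFAS excludes more than 10% of the FAS". The primary analysis itself uses the FAS (SAP Section 4.2).

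**The concern.** Criterion 1 names the active drug where its neighbour names the study intervention. Protocol Section 6.1 lists ALXN2050 and matching placebo as two interventions, and Table 11 gives the placebo group placebo tablets only. IgAN placebo participants switch to ALXN2050 with the Week 26 dose, after the period that criterion 1 covers. Suppose a placebo participant and a 180 mg participant each miss 30% of their tablets because of COVID-19. As written, only the second leaves the mFAS.

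The mFAS analysis is meant to show whether COVID-19 disruption affected the primary result. An exclusion rule that depends on the arm weakens it for that purpose. It also has a practical defect: deciding who meets the rule requires knowing who was assigned ALXN2050, at a time when the study team should still be blinded.

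**Working it through.** The plan states no figure for this rule, so there is none to reproduce. The check is whether the rule can be met in each arm, what it does to the trigger, and when it biases the comparison.

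**1. Can the rule be met?** SAP Section 4.5.1 defines expected total dose as assigned dose × 2 per day × days. Over 26 × 7 = 182 days:

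| Arm | Assigned ALXN2050 | 20% of it | Can more than 20% be missed? |
|---|---|---|---|
| 180 mg bid | 180 × 2 × 182 = 65,520 mg | 13,104 mg | Yes |
| 120 mg bid | 120 × 2 × 182 = 43,680 mg | 8,736 mg | Yes |
| Placebo | 0 mg | 0 mg | No: at most 0 mg can be missed |

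In tablets, every arm has 6 × 182 = 1,092 expected, and 20% is 218.4. A tablet rule therefore excludes anyone who missed 219 or more because of COVID-19, whatever the arm.

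**2. A related trap in milligrams.** SAP Section 4.5.1 also sets received dose to 60 mg × tablets received. In the 120 mg arm one tablet in three is placebo (Protocol Table 11), so that formula overstates the active dose. If it fed criterion 1, received dose would fall below 80% of expected only after a fraction 1 − 0.8 × 240/360 = 46.7% of tablets was missed. At 180 mg the fraction is 1 − 0.8 × 360/360 = 20%.

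**3. The trigger.** Take the FAS to equal the planned cohorts (assumption).

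- LN: 10% of 70 is 7, so at least 8 exclusions are needed.
- IgAN: 10% of 56 is 5.6, so at least 6 are needed.
- Under the literal rule, criterion 1 alone would have to find these among the active arms: 8 of 40 (20%) in LN and 6 of 32 (18.75%) in IgAN.
- If 10% of each LN arm were affected (assumption), the literal rule removes 3 + 1 = 4 of 70 (5.7%). A tablet rule removes 3 + 1 + 3 = 7 of 70 (10.0%). Neither exceeds 10%, so the analysis would also need exclusions under criteria 2 to 4.

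**4. When does one-sided removal bias the comparison?** Let the mean log change among unaffected participants be a on 180 mg and p on placebo. Let a fraction f in each arm be affected, with log change worse (higher) by d in both.

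- Nobody removed: (a + fd) − (p + fd) = a − p.
- Affected participants removed from both arms: a − p.
- Affected participants removed from 180 mg only: a − (p + fd) = (a − p) − fd.

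The error is −fd. With f = 0.10:

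- d = 0.2: shift −0.02; exp(−0.02) = 0.98, a GMR about 2% lower.
- d = 0.6: shift −0.06; exp(−0.06) = 0.94, a GMR about 6% lower.
- d = 0: no shift. A negative d reverses the sign.

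Against the planning SD of log change of 0.60, this range of d is one third of an SD to one full SD.

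**The case against.** The strongest reply is that the authors meant the blinded tablets. The protocol does use the drug name loosely. Section 6.1 tells participants attending PK visits, who are blinded, to hold their ALXN2050 dose. Sections 6.5.2 and 6.5.4 speak of stopping ALXN2050 before a calcineurin inhibitor, where Section 8.1.9 says study intervention. Tablets look identical, every arm takes six a day, and SAP compliance is counted in tablets without regard to arm. This makes the neutral reading plausible. It does not settle the text, because the SAP never says so and uses the neutral term for the same idea elsewhere in Table 2. Two programmers could build two different sets.

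A reader might also infer more than the documents support:

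- **That missed dosing in general is removed from the active arms only.** Criterion 1 is limited to doses missed because of COVID-19. Criteria 2 to 4 can remove placebo participants, and the Per-Protocol Set handles general under-dosing identically in every arm.
- **That the rule necessarily favours ALXN2050.** Step 4 of the working shows no bias unless affected participants differ in prognosis, and the sign follows that difference.
- **That the size is about 4%.** One could assume that under-dosed 180 mg participants in LN respond like placebo and compute 0.10 × (ln 0.60 − ln 0.40) = 0.041. That is the effect of removing under-dosed active participants at all. Removing placebo participants as well leaves the placebo ratio at 0.60 under the same assumption, so the GMR is 0.40/0.60 = 0.667 with or without the correction.
- **That the trial's main result is at risk.** It is not, because the primary analysis does not use the mFAS.

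**Conclusion.** The point holds as a minor drafting defect with a real but confined consequence. Applied as written, criterion 1 makes mFAS membership depend on the arm and cannot be decided blind. The damage is limited to one supplementary analysis that may never be run, and to the trigger for running it. The primary, per-protocol and treatment-policy analyses do not depend on this wording.

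The 0.02 to 0.06 shift in the log GMR rests on two assumptions that the documents do not supply: that 10% of each arm is affected, and that the prognostic difference is the same in both arms and lies between 0.2 and 0.6. It shows how large the error could be; it does not forecast it.

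**What to change.** In SAP Section 3, Table 2, mFAS criterion 1, replace the reference to the total assigned ALXN2050 dose with planned doses of study intervention (ALXN2050 or placebo), counted in tablets at 6 per day in every arm. Keep the 20% threshold, the COVID-19 condition and the 26-week period.

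The rule then matches the Per-Protocol Set, treats all arms alike, avoids the milligram problem in the 120 mg arm, and can be applied before database lock without unblinding. The cost is a few words in the SAP, provided the change is made before mFAS membership is settled. No new data are needed, since tablet counts are already collected.
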